Table 2-1. Schedule of Activities

PROCEDURE	Screening			Treatment Period (Weeks) ^a											Follow-up		Notes
	≤ 28 days	≤ 14 days	≤ 72 hr	0	3	6	9	12	15	18	21	24	>24 ^b	Safety (30 [+7] days post last dose) ^c	Survival ^d		
Swab of herpetic lesion for qPCR				X											X	Upon notification of a suspected herpetic lesion by the subject, the subject should be instructed to return to clinic within 3 days of the occurrence of reportable lesion suspected to be herpetic in origin such as cold sores or vesicles. The lesion should be evaluated by the investigator and swabbed if HSV infection is suspected. The sample will be collected, stored, and ultimately tested for the detection of talimogene laherparepvec DNA using qPCR.	
OPTIONAL PHARMACOGENETIC ASSESSMENT																	
Optional pharmacogenetic assessments	X			X	X	X								X ^e		Additional samples are not collected for this part of the study. Assessments are performed on residual or back-up samples from other assessments. Additional informed consent is required.	
STUDY TREATMENT																	
Talimogene laherparepvec				X	X	X	X	X	X	X	X	X	X	Q3W		The first dose of talimogene laherparepvec will be up to 4.0 mL of 10 ⁶ PFU/mL by intralesional injection. Subsequent doses of up to 4.0 mL of 10 ⁸ PFU/mL should be given Q3W until confirmed iCR, disappearance of all injectable lesions, documented confirmed iPD per modified irRC-RECIST, intolerance of study treatment, or 102 weeks from the first dose of talimogene laherparepvec, whichever occurs first.	

Footnotes defined on next page

Table 2-1. Schedule of Activities

PROCEDURE	Screening			Treatment Period (Weeks) ^a											Follow-up		Notes
	≤ 28 days	≤ 14 days	≤ 72 hr	0	3	6	9	12	15	18	21	24	>24 ^b	Safety (30 [+7] days post last dose) ^c	Survival ^d		
STUDY TREATMENT (CONTINUED)																	
Pembrolizumab				X	X	X	X	X	X	X	X	X	X	Q3W			Pembrolizumab at a dose of 200 mg will be administered intravenously every 3 weeks (+ 3 days for week 3, ± 3 days after week 3) thereafter until documented confirmed iPD per modified irRC-RECIST, intolerance of study treatment, or 102 weeks from the first dose of pembrolizumab, whichever occurs first.
REPORTING EXPOSURE TO TALIMOGENE LAHERPAREPVEC																	
Exposure of healthcare provider or close contact				X—————X													

aPTT = activated partial thromboplastin time; BRAF^{v600} = serine/threonine protein kinase BRAF V600; CR = complete response; CRF = case report form;

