CT = computed tomography; ECG = electrocardiogram; ECOG PS = Eastern Cooperative Oncology Group Performance Status; FT3 = free triiodothyronine; FT4 = free thyroxine; HSV = herpes simplex virus; INR = international normal; iCR = complete response (by modified irRC-RECIST); iPD = progressive disease (by modified irRC-RECIST); irRC-RECIST = immune-related Response Criteria simulating Response Evaluation Criteria in Solid Tumors; iSD = stable disease (by modified irRC-RECIST); LDH = lactate dehydrogenase; MRI = magnetic resonance imaging; PD = progressive disease; PD-L1 = programmed cell death-1 ligand 1; PET = positron emission tomography; PR = partial response; PT = prothrombin time; PTT = partial thromboplastin time; Q3W = once every 3 weeks; Q6W = once every 6 weeks; Q12W = once every 12 weeks; qPCR = real-time polymerase chain reaction; RECIST = Response Evaluation Criteria in Solid Tumor; T3 = triiodothyronine; TSH = thyroid-stimulating hormone

^a During the treatment period, assessments and procedures will be performed within ± 3 days of the planned visit except where noted. **(Note: the -3 day window does not apply to week 0 and all assessments should be completed following enrollment, using the + 3 day window for the first dose as described in Section 7, if required).**

^b Each subject will continue in the treatment period with study visits conducted Q3W up to week 102 or until there is a confirmed complete response or confirmed disease progression per modified irRC-RECIST, unacceptable toxicity, or no injectable disease (pembrolizumab administration can continue if talimogene laherparepvec is discontinued due to no injectable disease). Assessments will be performed at the frequencies noted within the respective rows in the table.

^c Safety follow-up will be performed approximately 30 (+ 7) days after the last dose of talimogene laherparepvec or pembrolizumab, whichever is later.

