At baseline, if there are \geq 2 lesions, 1 lesion (ie, the lesion considered lowest priority for injection) amenable for biopsy should be left uninjected at least until it is biopsied at week 6. Aside from leaving 1 lesion uninjected, all other reasonably injectable lesions

(cutaneous, subcutaneous and nodal disease that can be injected with or without ultrasound guidance) should be injected with the maximum dosing volume available on an individual dosing occasion (Table 7-1). On each treatment day, prioritization of injections is recommended as follows:

- any tumor that does not correspond to the uninjected lesion reserved for biopsy until week 6
- any new injectable tumor that has appeared since the last injection
- by tumor size, beginning with the largest tumor
- any previously uninjectable tumor(s) that is now injectable

It is recommended that each lesion should receive the maximum amount possible to inject due to tumor properties at each visit before moving on to the next lesion, using the prioritization model above and the injection volume guideline based on tumor size per Table 7-1. Lesions should be injected until the maximum volume per day (4.0 mL) has been reached or there are no further injectable lesions, whichever comes first.

Subjects will be treated with talimogene laherparepvec until disappearance of all injectable lesions, documented confirmed iPD per modified irRC-RECIST, intolerance of study treatment, or 102 weeks from the first dose of talimogene laherparepvec, whichever occurs first. Due to the mechanism of action, subjects may experience growth in existing tumors or the appearance of new tumors prior to maximal clinical benefit of talimogene laherparepvec. Therefore, talimogene laherparepvec dosing should continue provided that the subject has no evidence of confirmed iPD per modified irRC-RECIST and is able to tolerate the treatment. The dose, start date, and lot number of talimogene laherparepvec are to be recorded on the electronic CRF as per the recommendation found in the electronic CRF specific instructions.

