7.1.2.1 Pembrolizumab Dosage, Administration, and Schedule

Pembrolizumab is supplied as pembrolizumab 100 mg/4 mL vials (25 mg/mL) solution for IV infusion. Pembrolizumab at a dose of 200 mg will be administered IV every 3 weeks (+ 3 days for week 3, ± 3 days after week 3).

Pembrolizumab will be administered as a dose of 200 mg using a 30-minute IV infusion. Sites should make every effort to target infusion timing to be as close to 30 minutes as possible. However, given the variability of infusion pumps from site to site, a window between -5 minutes and +10 minutes is permitted (ie, infusion time is 30 minutes (-5 min/+10 min). Details on the preparation and administration are provided in the IPIM.

Pembrolizumab treatment will continue until subjects have documented confirmed iPD per modified irRC-RECIST, intolerance of study treatment, or 102 weeks from the first dose of pembrolizumab, whichever occurs first. **For subjects who have attained a confirmed CR, discontinuation of treatment may be considered if the subjects have been treated for at least 24 weeks with pembrolizumab and had at least 2 treatments with pembrolizumab beyond the date when the initial CR was declared.** The dose, start date, and lot number are to be recorded on the electronic CRF as per the recommendation found in the electronic CRF specific instructions.

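### Table 2-1 footnote b ends treatment at a confirmed complete response, but the pembrolizumab row and section 7.1.2.1 do not, so complete responders have contradictory pembrolizumab stop rules

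*Protocol*

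**What the plan says.** Three current passages of the protocol govern pembrolizumab after a complete response.

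- **Table 2-1, footnote b (section 2.2).** The treatment period runs "up to week 102 or until there is a confirmed complete response or confirmed disease progression per modified irRC-RECIST", or until unacceptable toxicity or no injectable disease. A parenthesis adds that "pembrolizumab administration can continue if talimogene laherparepvec is discontinued due to no injectable disease".
- **Table 2-1, pembrolizumab row.** Dosing continues "thereafter until documented confirmed iPD per modified irRC-RECIST, intolerance of study treatment, or 102 weeks from the first dose of pembrolizumab, whichever occurs first". Complete response is not listed.
- **Section 7.1.2.1.** Dosing continues "until subjects have documented confirmed iPD per modified irRC-RECIST, intolerance of study treatment, or 102 weeks from the first dose of pembrolizumab". Once CR is confirmed, stopping becomes optional: "discontinuation of treatment may be considered if the subjects have been treated for at least 24 weeks with pembrolizumab". The second condition is that two or more further doses were given after CR was first declared.

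For talimogene, the Table 2-1 row gives doses "until confirmed iCR, disappearance of all injectable lesions", followed by further stops. Section 7.1.1.1 says "Subjects will be treated with talimogene laherparepvec until disappearance of all injectable lesions", followed by confirmed iPD, intolerance or 102 weeks. It does not list a confirmed iCR.

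**The concern.** The same event, a confirmed complete response, ends treatment in the footnote, is not a stop in the row, and is an optional, conditional stop in section 7.1.2.1. Sites following different passages could treat otherwise identical complete responders differently, each believing that it follows the protocol.

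The statistical consequences come through the date of last dose:

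- **Exposure.** SAP 9.6.7 summarises pembrolizumab doses and the time from first to last dose.
- **Safety visit.** Footnote c to Table 2-1 sets it about 30 days after the last dose of either product.
- **Event windows.** SAP section 5 counts treatment-emergent adverse events to 30 days after last administration. Serious events count to 90 days, or to 30 days if new anticancer therapy starts.
- **Disposition.** SAP 9.2 tabulates reasons for ending treatment, but the reasons in Protocol 8.1 do not include complete response. Stops made under footnote b may therefore not be identifiable in that table.

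**Working it through.** The plan gives no figure to reproduce. The check is a comparison of passages plus visit arithmetic.

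**Step 1. What each passage does at a confirmed CR**

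| Place | Applies to | Effect of confirmed CR |
|---|---|---|
| Table 2-1, footnote b | Treatment period as a whole | Ends it |
| Table 2-1, pembrolizumab row | Pembrolizumab | None listed |
| Section 7.1.2.1 | Pembrolizumab | Stopping optional once two conditions are met |
| Table 2-1, talimogene row | Talimogene | Ends dosing |
| Section 7.1.1.1 | Talimogene | None listed; stops when all injectable lesions have disappeared |

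The first three rows cannot all hold for pembrolizumab. The last two differ in wording, and step 4 shows how little that matters.

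**Step 2. Size for pembrolizumab**

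Inputs: dosing every 3 weeks from week 0 with a limit of 102 weeks (Table 2-1); scans at weeks 12 and 24 and every 12 weeks after that (Table 2-1); confirmation of iCR at least 28 days later (Appendix 10, Table 12-7). Assumptions: no missed doses, the dose on the day of confirmation is given, and week 102 is dosed.

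- Doses from week 0 through week 102: 102/3 + 1 = 35.
- CR at week 12, confirmed at week 24. Doses through week 24: 24/3 + 1 = 9. Difference: 35 − 9 = **26 doses** (weeks 27 to 102; check: (102 − 27)/3 + 1 = 26).
- CR at week 24, confirmed at week 36. Doses through week 36: 36/3 + 1 = 13. Difference: 35 − 13 = **22 doses**.

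Withholding the dose on the day of confirmation adds one to each difference; not dosing at week 102 removes one. All are ceilings, because 7.1.2.1 allows stopping before week 102.

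**Step 3. Are the section 7.1.2.1 conditions met in these cases?**

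- Confirmation at week 24: 24 weeks of treatment are reached, and the doses after week 12 are those at weeks 15, 18 and 21 (three, or four with week 24). Both conditions are met. Stopping satisfies every passage; continuing satisfies the row and 7.1.2.1 but not footnote b.
- Off-schedule case: CR at week 24 and an extra scan at the 4-week minimum, week 28. Only the week 27 dose falls after the CR, so the two-treatment condition is not met. Footnote b ends treatment when 7.1.2.1 does not yet offer the option.

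In the first case, with last dose at week 24 in one reading and week 102 in the other, every window counted from last dose moves by 102 − 24 = 78 weeks.

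**Step 4. Talimogene**

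Modified iCR requires that all lesions disappear, so a subject with confirmed iCR has normally already met the 7.1.1.1 stop. The exception is nodal: Table 12-8, footnote e, accepts nodes below 10 mm short axis as iCR, nodal lesions may be injected, and Table 7-1 gives volumes for lesions of 0.5 cm and below. Only a residual node that is still injectable separates the two talimogene statements.

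**The case against.** **The footnote can be read in harmony with the rest.** A complete responder usually has no injectable disease, so the parenthesis could be taken to let pembrolizumab continue. This softens the conflict but does not remove it. Confirmed CR is a separate end point in the footnote, and the parenthesis is tied to talimogene stopping for a different stated reason. It also fails where a small residual node is still injectable.

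**The footnote hangs on the column for visits after week 24.** If it governs only those visits, confirmations before week 24 fall outside it. The cases in the working concern doses after week 24, so they stand.

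**Response rates are safe.** A reader might infer that ORR or CRR is distorted. The documents do not support that. Under SAP section 5, BOR by modified RECIST 1.1 needs no confirmation, and iCRR is settled once iCR is confirmed, so both are fixed by the time a stop at confirmed CR could apply.

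**Duration endpoints are only indirectly exposed.** A reader might infer that the contradiction makes DOR and DRR uninterpretable. DOR runs to progression or death and is not censored when treatment stops, and 12-weekly imaging is to continue after stopping for reasons other than confirmed iPD. Optional stopping under 7.1.2.1 would leave mixed treatment lengths even if the footnote were aligned with it. What remains is any true effect of shorter treatment on durability, which the documents do not quantify.

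**The amendment history.** The Amendment 3 rationale says that language was changed to let pembrolizumab continue after a complete response. A reader might infer that this proves the conflict or settles which rule governs. It does neither: a change log describes changes, and the conflict rests on the current text alone.

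**Conclusion.** The protocol contradicts itself on pembrolizumab after a confirmed complete response. Footnote b requires an end to treatment, the pembrolizumab row contains no such stop, and section 7.1.2.1 makes it optional and conditional. On the planned scan schedule, the readings differ by up to about 26 doses for a CR first seen at week 12 and about 22 for one first seen at week 24. Both figures assume no missed doses and dosing through week 102.

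The consequence lies in exposure, the safety visit and the TEAE and TESAE windows. DOR and DRR are affected only through a real effect of treatment length; ORR and CRR are not materially affected. Only complete responders are concerned, and the documents give no count of them. All analyses are descriptive, so no test or error rate is at stake.

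The talimogene mismatch is minor. A reader might infer an equally contradictory rule there, but the iCR definition makes the two statements coincide except for a residual injectable node below 10 mm.

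**What to change.** - Reconcile footnote b with the pembrolizumab row and section 7.1.2.1, and the talimogene row with section 7.1.1.1, so that each product has one statement of what happens at a confirmed complete response. This review takes no position on which rule is right.
- Optionally, list in the study report, for each complete responder: date of CR, date of confirmation, last dose of each product, and reason for stopping. The planned disposition and exposure summaries cover part of this, but not subject by subject.

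Cost: one protocol clarification and, if wanted, one listing from doses, dates and response data already collected. No endpoint definition or sample size changes.

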3.1 Study Rationale

3.1.1 Rationale for Combination Therapy of Talimogene Laherparepvec and Pembrolizumab in Stage IIIB-IVM1d Unresectable Melanoma Following Progression on a Prior PD-1 Therapy

Historical studies referenced in Section 3.1 to Section 3.3 refer to melanoma staging using the American Joint Committee on Cancer (AJCC) ed. 7 (seventh edition of the AJCC Cancer Staging Manual [Gershenwald et al, 2017]) or earlier editions, while the current study refers to melanoma staging using the AJCC ed. 8 (eighth edition of the AJCC Cancer Staging Manual [Gershenwald et al, 2017]).

Anti-programmed cell death-1 (PD-1) therapies, pembrolizumab and nivolumab, are currently considered the standard of care for advanced melanoma in the first line metastatic setting. For patients who fail anti-PD-1 therapy, treatment options are limited in advanced melanoma following disease progression during or after anti-PD-1 therapy, thus it is considered an unmet medical need. In patients with advanced metastatic melanoma who harbor a BRAF V600 mutation, both immunotherapy and targeted therapy are recommended as first line treatment in the metastatic setting (ESMO, 2019; NCCN, 2019). National Comprehensive Cancer Network (NCCN) guidelines recommend that targeted therapy is preferred when a rapid clinical response is desired, and treatment continue until maximum clinical benefit is reached.

Additionally, for those treated with a BRAF target therapy who have achieved maximum clinical benefit (but not complete remission) a switch to immune checkpoint inhibitor therapy may be considered. Therefore, this protocol allows prior BRAF/MEK inhibitor therapy if clinically indicated but does not mandate prior progression on BRAF/MEK inhibitor. If these patients progress on or after anti-PD-1 therapy, they are also considered an unmet medical need.

Additionally, with the recent availability of checkpoint inhibitors in the adjuvant setting, it remains to be understood how patients will be treated upon progression to metastatic disease. The purpose of this study is to explore the safety and efficacy of the talimogene laherparepvec and pembrolizumab combination in patients with unresectable, injectable metastatic IIIB-IVM1d melanoma who have progressed following anti-PD-1 therapy.

Talimogene laherparepvec and PD-1 blockade likely play complementary roles in regulating adaptive immunity. Talimogene laherparepvec likely augments dendritic cell-mediated tumor antigen presentation through local expression of

granulocyte-macrophage colony-stimulating factor (GM-CSF) (Kaufman et al, 2010) and local antigen release by direct tumor lysis. Pembrolizumab prevents T-cell exhaustion in peripheral tissues. The combination of an agent that increases tumor-specific immune activation with 1 that blocks inhibitory T-cell checkpoints could produce greater antitumor activity than either agent alone.

The combination of talimogene laherparepvec and pembrolizumab in the first line metastatic setting is being investigated in the MASTERKEY-265 phase 1b/3 study in subjects with unresectable/metastatic IIIB-IVM1c melanoma. The phase 1b portion of the study enrolled 21 subjects who received talimogene laherparepvec and pembrolizumab in combination to establish the safety of the combination. There were no unanticipated safety signals observed with the combination of talimogene laherparepvec and pembrolizumab. At the time of the phase 1b 6-month primary analysis, the confirmed objective response rate (ORR) and complete response rate (CRR) were 57.1% and 23.8%, respectively, per immune-related Response Criteria (irRC). Median PFS was not reached, with 71% of subjects not having progressed at 6 months (Long et al, 2016). Baseline and on therapy biopsies of talimogene laherparepvec injected lesions, showed that the combination of talimogene laherparepvec and pembrolizumab changed the tumor microenvironment by increasing the CD8+ T cell infiltration. The response was independent of the baseline CD8+ T cell density. Of the 13 patients with CD8+ density < 1,000 cells/mm² at baseline, 9 patients responded to the combination therapy and 4 patients had disease progression (Ribas et al, 2017). These results of the phase 1b study supported continuation of the phase 3 portion of the MASTERKEY-265 study which is a randomized trial comparing talimogene laherparepvec and pembrolizumab combination to pembrolizumab monotherapy. Enrollment is complete and treatment is ongoing.

Several retrospective analyses of the safety and clinical activity of various immunotherapies following progression on or shortly after anti-PD-1 therapy were reviewed (Gogas et al 2018, Long et al, 2017). In a retrospective analysis of the Keynote-006 study, 97 subjects were identified who progressed during pembrolizumab treatment and received ipilimumab in the first line of subsequent therapy. Of these 97 subjects, the median duration of time following the last dose of pembrolizumab to the first dose of ipilimumab was 5 weeks and the ORR reported for ipilimumab was 14% (best overall response of complete response [CR] in 3%, PR in 11%, stable disease [SD]

in 33%, progressive disease [PD] in 33%, and unknown in 23% of subjects) (Long et al, 2017).

A retrospective analysis evaluated talimogene laherparepvec monotherapy following progression on prior checkpoint inhibitor therapies in patients with unresectable Stage IIIB-IVM1c metastatic melanoma. In Studies 20120324 and 20120325, 17 and 26 patients, respectively, progressed on prior checkpoint inhibitors, including pembrolizumab, nivolumab, ipilimumab, or nivolumab/ipilimumab prior to enrolling on these studies. The ORR following talimogene laherparepvec was 24% (4 of 17 subjects) and 21% (6 of 26 subjects) including 1 CR (20110324) and 9 PRs (total in both 20120324 and 20120325). Although the retrospective analysis is limited, the ORR and safety observed in this subgroup following talimogene laherparepvec administration is consistent with the ORR observed in the phase 3 OPTiM trial and warrants further studies to understand if talimogene laherparepvec demonstrates clinical activity in the post PD-1 setting (Gogas et al, 2018).

This study is intended to provide additional clinical data to support the combination of talimogene laherparepvec and pembrolizumab in unresectable/metastatic IIIB-IVM1d melanoma specifically in patients who have progressed on prior anti-PD-1 based therapy.

In this study, talimogene laherparepvec will be administered every 3 weeks following the talimogene laherparepvec dosing schedule in Section 7.1.1.1 and pembrolizumab will be administered at a fixed dose of 200 mg every 3 weeks as per Pembrolizumab Investigator's Brochure.

3.2 Background

3.2.1 Disease

In adults, cutaneous melanoma is the fifth most common cancer in men and the seventh most common cancer in women in the United States of America (USA), with an estimated 96,480 new cases and 7,230 deaths expected in 2019 (Siegel et al, 2019). In Europe, the annual incidence of melanoma is somewhat lower than that in the USA, with a crude rate of approximately 15 per 100,000 as compared with 25 per 100,000 in the USA, but is the seventh most common cancer among women (Ferlay et al, 2018; Siegel et al, 2019). In Europe as a whole, approximately 144,200 new cases were diagnosed in 2018 (Ferlay et al, 2018). The incidence of melanoma is increasing rapidly worldwide, with a 270% increase in the USA between 1973 and 2002. This increase is

the most rapid of any cancer with the exception of lung cancer in women (Jemal et al, 2006; Ries et al, 2000).

Cancer has developed multiple mechanisms to successfully avoid recognition by the immune-system and resultant antitumor effector functions, thus limiting the benefits of cancer immunotherapies (Whiteside, 2006). Therapeutic strategies have recently been developed to overcome a tumor's ability to protect itself from targeted immune response. Antibodies that block the inhibitory receptor cytotoxic T-lymphocyte associated antigen 4 (CTLA-4), such as ipilimumab, have been shown to release 1 of these negative immune regulatory pathways, leading to durable responses in a subgroup of patients with metastatic melanoma and an overall survival (OS) benefit in patients with metastatic melanoma (Hodi et al, 2010; Robert et al, 2011).

The PD-1 receptor is another inhibitory receptor expressed by T cells. Its primary ligand, programmed cell death-1 ligand 1 (PD-L1), is frequently expressed within the tumor microenvironment, including cancer cells and tumor-infiltrating macrophages. The PD-1 receptor has a second ligand, programmed cell death-1 ligand 2 (PD-L2), which is preferentially expressed by antigen-presenting cells (Pardoll, 2012). In tumor models, PD-1 negatively regulates the effector phase of T-cell responses after ligation of PD-L1 expressed by the tumor (Blank et al, 2004). It has been postulated that antibodies that block the interaction between PD-1 and PD-L1 in tumors may preferentially release the cytotoxic function of tumor-specific T cells with fewer systemic toxic effects than those that are seen with other immune checkpoint inhibitors (Okazaki and Honjo, 2007; Pardoll, 2012; Ribas; 2012). Inhibitory antibodies targeted to PD-1 and PD-L1 have demonstrated objective responses in multiple tumor types including melanoma (Brahmer et al, 2012; Hamid et al, 2013; Robert et al, 2015a; Robert et al, 2015b). The combination of PD-1 blockade with nivolumab and CTLA-4 blockade with ipilimumab has resulted in longer PFS than either agent alone but was associated with a high rate of grade 3 or 4 adverse events (Larkin et al, 2015).

